7.5.1.1 Gastrointestinal Dose-limiting Toxicity

The following study treatment-related event will be considered a GI DLT:

• Grade ≥ 3 diarrhea or colitis, regardless of duration

7.5.1.2 Hepatic Dose-limiting Toxicity

Any of the following study treatment-related events will be considered a hepatic DLT:

- Grade 4 elevations in serum transaminases (AST and ALT), alkaline phosphatase (ALP), or total bilirubin.
- Grade 3 elevations in serum AST, ALT, or ALP that last longer than 5 days, or is associated with clinical symptoms, or bilirubin > 2× ULN in the absence of cholestasis.
- Grade 2 elevations in AST or ALT with symptomatic liver inflammation (eg, right upper quadrant tenderness, jaundice).
- AST or ALT > 3× ULN and concurrent total bilirubin > 2× ULN without initial findings of cholestasis (elevated ALP, eg, findings consistent with Hy's law or FDA definition of potential drug-induced liver injury [p-DILI]). Note that this specific category of DLT uses ULN rather than NCI CTCAE grade for definition.

Any of the following study treatment-related events will be considered a hepatic DLT for participants with HCC:

• ALT or AST > 15× ULN, regardless of duration.

- ALT or AST $> 10 \times$ ULN for greater than 2 weeks.
- Total bilirubin $> 8 \times$ ULN for participants with elevated bilirubin at study entry or $> 5 \times$ ULN for participants with normal bilirubin at study entry, regardless of duration.
- ALT $> 10 \times$ ULN and concurrent total bilirubin $> 2 \times$ ULN.

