7.5.1.5 Other Dose-limiting Toxicities

Any of the following events will be considered a DLT:

- Grade \geq 4 hypersensitivity reaction or Grade 3 that does not resolve to Grade 1 in \leq 6 hours
- Grade 2 pneumonitis that does not respond to dose delay and systemic steroids within 14 days.
- Any death not clearly due to the underlying disease or extraneous causes
- Grade 2 drug-related uveitis, episcleritis, iritis, eye pain, or blurred vision that does not respond to topical therapy and does not improve to Grade 1 severity within 2 weeks OR requires systemic treatment.
- Grade 3 drug-related uveitis, episcleritis, iritis, pneumonitis, bronchospasm, or neurologic toxicity

Checkpoint inhibitor molecules, have been uncommonly associated with ocular drug-related AEs. Inflammation of components within the eye (eg, episcleritis, uveitis) are uncommon events of nivolumab or ipilimumab monotherapy (< 1% of cases). These events are usually of low or intermediate grade, reversible, detected early in the course of therapy and manageable with topical or systemic steroids.

- Routine eye examinations should be performed in participants receiving immune checkpoint inhibitors. Upon clinical suspicion of an ocular event consider ophthalmic consult, dose delay, or dose discontinuation
- Permanently discontinue for clinically significant or severe immune-mediated adverse reactions. Initiate systemic corticosteroids for severe immune-mediated adverse reactions
- For Grade 2-4 ophthalmologic reactions that require systemic treatment or that do not improve to Grade 1 within 2 weeks while receiving topical therapy, permanently discontinue
- Permanently discontinue for immune-mediated ocular disease that is unresponsive to local immunosuppressive therapy
- Administer corticosteroid eye drops to participants who develop uveitis, iritis, or episcleritis

Other ≥ Grade 3 study treatment-related toxicity will be considered a DLT. However, the following Grade 3-4 events will **not** be considered DLTs:

- Grade 3-4 electrolyte abnormalities that are not complicated by associated clinical adverse experiences, last less than 72 hours, and either resolve spontaneously or respond to conventional medical intervention.
- Grade 3 nausea or vomiting that lasts less than 48 hours and either resolves spontaneously or responds to medical intervention.
- Grade 3-4 elevation of amylase or lipase not associated with clinical or radiographic evidence of pancreatitis

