7.5.3 Dose Delays Due To Toxicity

If an event is attributed to BMS-986249, ipilimumab, or nivolumab, alone or in combination, then all study treatments must be delayed until treatment can resume (See Section 7.5.3.1). Tumor assessments for all participants should continue per protocol even if dosing is delayed. Participants who experience the following must have all study treatment(s) withheld:

- SARS-CoV-2 infection either confirmed or suspected
- Potential DLTs, until DLT relatedness is defined
- Drug-related select AEs and laboratory abnormalities as follows:
 - Any Grade ≥ 2 non-skin AE, with the following exceptions:
 - o Grade 2 drug-related fatigue or laboratory abnormalities do not require a treatment delay
 - Dose delay for AST, ALT, or total bilirubin abnormalities in HCC participants should be managed as follows:
 - o If baseline AST, ALT, or bilirubin is within normal limits, delay dosing for Grade ≥ 2 toxicity
 - o If baseline AST, ALT, or bilirubin is within the Grade 1 toxicity range, delay dosing for Grade ≥ 3 toxicity
 - o If baseline AST, ALT, or bilirubin is within the Grade 2 toxicity range, delay dosing for a 2-fold drug-related increase in AST, ALT, or bilirubin, or for AST, ALT, or bilirubin values 8× ULN (whichever is lower).
 - Grade 3 skin AE
 - Grade 3 laboratory abnormality, with the following exceptions:
 - o Grade 3 lymphopenia does not require a dose delay
 - ≥ Grade 3 amylase or lipase abnormality that is not associated with clinical manifestations or radiographic evidence of pancreatitis does not require dose delay
 - All troponin elevations require a dose delay

 AE, laboratory abnormality, or concurrent illness that, in the judgment of the investigator, warrants delaying study treatment administration

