8 DISCONTINUATION CRITERIA

8.1 Discontinuation from Study Treatment

Participants MUST discontinue IP for any of the following reasons:

- Documented disease progression as defined by RECIST v1.1 (Appendix 5) or PCWG3 (Appendix 6) unless participants meet criteria for treatment beyond progression (Section 8.1.1).
- Clinical deterioration while receiving active study therapy that, in the opinion of the investigator, indicates that continued participation in the study is not in the best interest of the participant.
- Any drug-related AE occurring at any time that meets DLT criteria as outlined in Section 7.5.1 will require permanent discontinuation. Exceptions to permanent discontinuation are listed in Section 7.5.4.
- Participant's request to stop study treatment. Participants who request to discontinue study treatment will remain in the study and must continue to be followed for protocol-specified

- follow-up procedures. The only exception to this is when a participant specifically withdraws consent for any further contact with him/her or persons previously authorized by participant to provide this information.
- Any clinical AE, laboratory abnormality or intercurrent illness which, in the opinion of the
 investigator, indicates that continued participation in the study is not in the best interest of the
 participant.
- Termination of the study by the Sponsor.
- Loss of ability to freely provide consent through imprisonment or involuntarily incarceration for treatment of either a psychiatric or physical (eg, infectious disease) illness. (Note: Under specific circumstances and only in countries where local regulations permit, a participant who has been imprisoned may be permitted to continue as a participant. Strict conditions apply and BMS approval is required).
- Inability to comply with protocol.
- Discretion of the investigator.
- Pregnancy.
- Individual participants with confirmed CR will be given the option to discontinue study therapy on a case by case basis after specific consultation and agreement between the investigator and Medical Monitor (or designee) in settings where benefit/risk justifies discontinuation of study therapy.
- Any event that leads to delay in dosing lasting > 8 weeks from the previous dose requires discontinuation, with the following exceptions:
 - Dosing delays for prolonged steroid tapers to manage drug-related AEs are allowed.

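### Section 7.5.1.2 puts HCC participants under two hepatic DLT lists with very different thresholds and does not say which one governs

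*Combined protocol and SAP*

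**What the plan says.** All references are to the combined protocol and SAP.

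- **7.5.1.2, general list.** The lead-in is "Any of the following study treatment-related events will be considered a hepatic DLT", with no limit by tumor type. Items include "Grade 3 elevations in serum AST, ALT, or ALP that last longer than 5 days" and "AST or ALT > 3× ULN and concurrent total bilirubin > 2× ULN without initial findings of cholestasis".
- **7.5.1.2, HCC list.** The lead-in is "Any of the following study treatment-related events will be considered a hepatic DLT for participants with HCC". Its AST/ALT items are "ALT or AST > 15× ULN, regardless of duration", a level above 10× ULN for more than 2 weeks, and ALT above 10× ULN together with bilirubin above 2× ULN.
- **7.5.1.5, catch-all.** "Other ≥ Grade 3 study treatment-related toxicity will be considered a DLT". None of the exceptions listed there concerns AST, ALT or bilirubin.
- **8.1, consequence.** "Any drug-related AE occurring at any time that meets DLT criteria as outlined in Section 7.5.1 will require permanent discontinuation". Section 7.5.1 says the same for every cycle and cohort, Part 2 included. The exceptions in 7.5.4 contain no AST, ALT or bilirubin item.
- **7.5.3, dose delays.** HCC participants have their own liver-test delay rule, graded by baseline. With a Grade 2 baseline it is to "delay dosing for a 2-fold drug-related increase in AST, ALT, or bilirubin, or for AST, ALT, or bilirubin values 8× ULN", taking the lower. The same section also withholds treatment for suspected DLTs while relatedness is settled, and for Grade 3 laboratory abnormalities. The exceptions to that last hold are lymphopenia and uncomplicated amylase or lipase elevation; HCC liver tests are not among them.
- **6.1, entry limits for HCC.** AST and ALT up to 5× ULN and bilirubin up to 3 mg/dL. Appendix 9 confirms that Grade 2 AST/ALT at entry is acceptable.
- **5.1.2.4, Part 2 monitoring.** A discussion about interrupting enrollment may follow if the posterior probability is at least 95% that the rate of treatment-related events meeting DLT criteria exceeds a threshold.

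**The concern.** Two sites could see the same liver-test course in an HCC participant and act in opposite ways, each following the text. A site that applies both lists stops treatment for good and records a DLT-criteria event. A site that applies only the HCC list does neither.

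That affects who stays on treatment in the HCC cohort (about 40 participants planned) and what the Part 2 toxicity rule counts. The general list's levels also lie close to, or overlap, what the cohort's entry criteria allow, so the conflict is not confined to remote cases.

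**Working it through.** The plan states no figure here to reproduce. The check sets the thresholds side by side. Grade bands are those in the general hepatic algorithm of Appendix 9: AST/ALT Grade 1 up to 3× ULN, Grade 2 above 3 to 5× ULN, Grade 3-4 above 5× ULN.

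**1. The two DLT lists**

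| Item | General list | HCC list |
|---|---|---|
| AST/ALT sustained | Grade 3 (> 5× ULN) for more than 5 days | > 10× ULN for more than 2 weeks |
| AST/ALT, any duration | Grade 4 | > 15× ULN |
| Combined with bilirubin > 2× ULN | AST or ALT > 3× ULN, no initial cholestasis | ALT > 10× ULN |

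**2. HCC delay level in 7.5.3 against the general list**

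Let b be baseline AST/ALT in multiples of ULN. The delay level D(b) is 3 if baseline is normal (Grade ≥ 2), 5 if baseline is Grade 1 (Grade ≥ 3), and min(2b, 8) if baseline is Grade 2.

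| Baseline | D(b) | D(b) − 5 |
|---|---|---|
| Normal | 3 | −2 |
| Grade 1 (above 1 to 3) | 5 | 0, with no 5-day wait |
| 3.1 | min(6.2, 8) = 6.2 | 1.2 |
| 3.5 | min(7.0, 8) = 7.0 | 2.0 |
| 4 to 5 | min(8 to 10, 8) = 8 | 3.0 |

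For the Grade 3 item, the HCC delay level exceeds the general-list level only for Grade 2 baselines, by more than 1 and up to 3× ULN.

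**3. One participant.** Baseline 4× ULN, rising to 6× ULN for 6 days, judged related:
- General list: 6 > 5 and 6 days > 5 days, so a DLT and permanent discontinuation.
- HCC list: 6 < 10, so not a hepatic DLT.
- HCC delay rule: 6 < min(8, 8) = 8, so no delay.
- General Grade 3 laboratory hold: 6 > 5, so withhold.

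The last two lines contradict each other within 7.5.3.

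**4. Combined item against entry limits.** With bilirubin ULN assumed to be 1.0 to 1.3 mg/dL, the 3 mg/dL entry limit is 3/1.3 = 2.3 to 3/1.0 = 3.0× ULN. Under Appendix 13, bilirubin of 3 mg/dL scores 2 points; with 1 point on each of the other four measures the total is 6, still Child-Pugh A. An eligible participant could therefore meet both numerical parts of the general combined item (AST/ALT above 3×, bilirubin above 2× ULN) at entry. It would become a DLT only if judged treatment-related and without initial cholestasis.

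**5. Order of hold and discontinuation**
- Literal reading throughout: treatment is held at Grade 3, or as a suspected DLT, before the 5-day criterion is complete. A combined-item event is held while relatedness is decided.
- HCC-specific reading throughout: the delay comes at 3 to 8× ULN, below the lowest AST/ALT-only DLT level of 10× ULN for more than 2 weeks.

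In both, the hold comes first.

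**6. Monitoring count.** If the rate is taken over 40 HCC participants, each one reclassified moves it by 1/40 = 2.5 percentage points. How many would be reclassified is not in the documents.

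**The case against.** The strongest reply is that the HCC list is plainly meant as a substitute. Section 6.1 gives platelet and hemoglobin limits with no HCC exclusion, then HCC values that clearly replace them. Section 9.2.8 does the same for potential drug-induced liver injury, explaining that the HCC definition allows for impaired baseline liver function. If the lists were additive, the two-week item would be redundant, since anyone meeting it would already have exceeded Grade 3 for 5 days. The catch-all sits under a heading for other toxicities, after hepatic events have had their own section; extending it to liver tests would also cancel the 5-day qualifier for everyone else.

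This makes replacement the likely intent, but the text does not say so, and elsewhere the protocol does write an explicit HCC exclusion (hepatic function in 6.1, chronic hepatitis in 6.2). Replacement alone also leaves loose ends. A related Grade 3 ALT of 6× ULN would then be on no hepatic list for HCC, and nothing says the catch-all passes over it. Section 7.5.3.1 requires permanent discontinuation for combined Grade 2 AST/ALT and bilirubin that meet DLT criteria, without excluding HCC, yet only the general list has such an item. The HCC algorithm in Appendix 9 refers sites to Sections 7.4.3 and 7.4.3.1 for delay and resumption, but 7.4 is now Blinding.

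A reader might go further and infer that an HCC participant could be permanently discontinued before any dose is held. That requires reading the DLT lists literally while letting the HCC delay rule displace the general holds. Step 5 shows that neither consistent reading gives that result.

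It is also fair that the statistical reach is limited. The Part 2B primary endpoint, treatment-related Grade 3-5 events within 24 weeks, is not defined through DLT status. The Bayesian rule is optional, investigators and sponsor confer at least monthly during expansion, and tumor assessments continue after discontinuation.

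**Conclusion.** The point holds as a conflict between stated rules. Section 7.5.1.2 leaves open which hepatic DLT list governs HCC participants, and the answer decides permanent discontinuation over a wide range: from above 5× ULN for more than 5 days (or above 3× with raised bilirubin) to above 10× for more than 2 weeks or above 15×. The mismatch between the HCC delay level and the general list's Grade 3 item is confined to Grade 2 baseline AST/ALT. It comes with a second conflict, between that delay level and the general Grade 3 laboratory hold.

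The HCC contribution to the Part 2 toxicity count depends on the list applied, but by how much cannot be derived. A reader might apply the Grade 3-4 AST/ALT frequencies in Section 3.2.4 to 40 participants. Those come from 53 melanoma participants on several ipilimumab and nivolumab dose combinations, pool Grades 3 and 4, and give no duration, so they do not show how many HCC participants would fall between the lists.

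The verdict rests on the Appendix 9 grade bands and, for step 4 only, on the assumed bilirubin ULN. It takes no view on which thresholds are clinically right.

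**What to change.** Reconcile 7.5.1.2, 7.5.1.5, 7.5.3 and 8.1:

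- In 7.5.1.2, state whether the HCC list replaces the general hepatic list or adds to it.
- In 7.5.1.5, state whether the catch-all reaches AST, ALT and bilirubin in HCC participants.
- In 7.5.3, state whether the general Grade 3 laboratory hold applies to HCC liver tests or gives way to the baseline-graded rule.
- Align 8.1 and the combined Grade 2 item in 7.5.3.1 with the result, and correct the section references in the HCC algorithm of Appendix 9.
- In 5.1.2.4, state that the Part 2 monitoring count classifies HCC hepatic events by that single definition.

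The thresholds are for the sponsor's clinicians to decide. The cost is a short protocol clarification with no new data collection. HCC hepatic events already classified should be checked once against the settled definition.

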7.5.1.3 Hematologic Dose-limiting Toxicity

Any of the following study treatment-related events will be considered a hematologic DLT:

- Grade 4 neutropenia ≥ 7 days in duration
- Grade 4 thrombocytopenia
- Grade 3 thrombocytopenia with bleeding or any requirement for platelet transfusion
- Grade 3 hemolysis (ie, requiring transfusion or medical intervention such as steroids)
- Neutropenic fever of any duration
- Grade 4 anemia not explained by underlying disease

7.5.1.4 Dermatologic Dose-limiting Toxicity

Any of the following study treatment-related events will be considered a dermatologic DLT:

- Grade 4 rash
- Grade 3 rash if no improvement (ie, resolution to ≤ Grade 1) after a 1- to 2-week infusion delay

7.5.1.5 Other Dose-limiting Toxicities

Any of the following events will be considered a DLT:

- Grade \geq 4 hypersensitivity reaction or Grade 3 that does not resolve to Grade 1 in \leq 6 hours
- Grade 2 pneumonitis that does not respond to dose delay and systemic steroids within 14 days.
- Any death not clearly due to the underlying disease or extraneous causes
- Grade 2 drug-related uveitis, episcleritis, iritis, eye pain, or blurred vision that does not respond to topical therapy and does not improve to Grade 1 severity within 2 weeks OR requires systemic treatment.
- Grade 3 drug-related uveitis, episcleritis, iritis, pneumonitis, bronchospasm, or neurologic toxicity

Checkpoint inhibitor molecules, have been uncommonly associated with ocular drug-related AEs. Inflammation of components within the eye (eg, episcleritis, uveitis) are uncommon events of nivolumab or ipilimumab monotherapy (< 1% of cases). These events are usually of low or intermediate grade, reversible, detected early in the course of therapy and manageable with topical or systemic steroids.

- Routine eye examinations should be performed in participants receiving immune checkpoint inhibitors. Upon clinical suspicion of an ocular event consider ophthalmic consult, dose delay, or dose discontinuation
- Permanently discontinue for clinically significant or severe immune-mediated adverse reactions. Initiate systemic corticosteroids for severe immune-mediated adverse reactions
- For Grade 2-4 ophthalmologic reactions that require systemic treatment or that do not improve to Grade 1 within 2 weeks while receiving topical therapy, permanently discontinue
- Permanently discontinue for immune-mediated ocular disease that is unresponsive to local immunosuppressive therapy
- Administer corticosteroid eye drops to participants who develop uveitis, iritis, or episcleritis

Other ≥ Grade 3 study treatment-related toxicity will be considered a DLT. However, the following Grade 3-4 events will **not** be considered DLTs:

- Grade 3-4 electrolyte abnormalities that are not complicated by associated clinical adverse experiences, last less than 72 hours, and either resolve spontaneously or respond to conventional medical intervention.
- Grade 3 nausea or vomiting that lasts less than 48 hours and either resolves spontaneously or responds to medical intervention.
- Grade 3-4 elevation of amylase or lipase not associated with clinical or radiographic evidence of pancreatitis
- Grade 3 fever not associated with hemodynamic compromise (eg, hypotension, clinical or laboratory evidence of impaired end-organ perfusion)
- Grade 3 endocrinopathy that is well controlled by hormone replacement
- Grade 3 tumor flare (defined as pain, irritation, or rash that localizes to sites of known or suspected tumor)
- Grade 3 fatigue lasting < 1 week
- Grade 3 infusion reaction that returns to Grade 1 in < 6 hours

7.5.2 Management Algorithms for Immuno-oncology Agents

I-O agents are associated with irAEs that can differ in severity and duration from AEs caused by other therapeutic classes. BMS-986249, ipilimumab, and nivolumab are considered I-O agents in this protocol. Early recognition and management of irAEs associated with I-O agents may mitigate severe toxicity. Management algorithms have been developed from extensive experience with ipilimumab and nivolumab to assist investigators in assessing and managing the following groups of irAEs:

- GI
- Renal
- Pulmonary

- Hepatic
- Endocrinopathies
- Skin
- Neurological (including encephalitis)
- Myocarditis

The clinical nature of AEs noted with BMS-986249 will determine the role of the algorithms for use in toxicities related to its use in this study. The standard algorithms recommended for the management of irAEs in this protocol are in Appendix 9.

GI AE management for BMS-986249 Grade 2 diarrhea/colitis irAEs may require earlier initiation of steroids.

7.5.3 Dose Delays Due To Toxicity

If an event is attributed to BMS-986249, ipilimumab, or nivolumab, alone or in combination, then all study treatments must be delayed until treatment can resume (See Section 7.5.3.1). Tumor assessments for all participants should continue per protocol even if dosing is delayed. Participants who experience the following must have all study treatment(s) withheld:

- SARS-CoV-2 infection either confirmed or suspected
- Potential DLTs, until DLT relatedness is defined
- Drug-related select AEs and laboratory abnormalities as follows:
 - Any Grade ≥ 2 non-skin AE, with the following exceptions:
 - o Grade 2 drug-related fatigue or laboratory abnormalities do not require a treatment delay
 - Dose delay for AST, ALT, or total bilirubin abnormalities in HCC participants should be managed as follows:
 - o If baseline AST, ALT, or bilirubin is within normal limits, delay dosing for Grade ≥ 2 toxicity
 - o If baseline AST, ALT, or bilirubin is within the Grade 1 toxicity range, delay dosing for Grade ≥ 3 toxicity
 - o If baseline AST, ALT, or bilirubin is within the Grade 2 toxicity range, delay dosing for a 2-fold drug-related increase in AST, ALT, or bilirubin, or for AST, ALT, or bilirubin values 8× ULN (whichever is lower).
 - Grade 3 skin AE
 - Grade 3 laboratory abnormality, with the following exceptions:
 - o Grade 3 lymphopenia does not require a dose delay
 - ≥ Grade 3 amylase or lipase abnormality that is not associated with clinical manifestations or radiographic evidence of pancreatitis does not require dose delay
 - All troponin elevations require a dose delay

 AE, laboratory abnormality, or concurrent illness that, in the judgment of the investigator, warrants delaying study treatment administration

Participants who require a delay of study treatment should be re-evaluated weekly or more frequently if clinically indicated. For participants receiving a combination (eg, Part 1B and Part 2), if dosing is delayed, then both study treatments must be delayed together. If dosing with both study treatments is to be resumed after a delay, then both must be resumed on the same day. Criteria for participants who are required to permanently discontinue study treatments are listed in Section 8.2. In addition, all Grade 2 GI, renal, pulmonary, hepatic, and neurological AEs should be evaluated and managed per the toxicity management algorithms in Appendix 9. Participants not meeting guidelines for permanent discontinuation will be permitted to resume therapy based on the criteria specified below in Section 7.5.3.1. Participants eligible to resume study therapy will resume study therapy at the nominal treatment visit after their last received study medication dose.

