Patients on IV steroids may be switched to an equivalent dose of oral corticosteroids (e.g. prednisone) at start of tapering or earlier, once sustained clinical improvement is observed. Lower bioavailability of oral corticosteroids should be taken into account when switching to the equivalent dose of oral corticosteroids

25-Jun-2019

Protocol Amendment No.: 09 Date: 14-Mar-2023

Hepatic Adverse Event Management Algorithm

Rule out non-inflammatory causes. If non-inflammatory cause, treat accordingly and continue I-O therapy. Consider imaging for obstruction.

Grade of Liver Test Management Follow-up Elevation (NCI CTCAE v4) Grade 1 · Continue LFT monitoring per protocol AST or ALT > ULN to 3.0 x · Continue I-O therapy per protocol If worsens: ULN and/or T. bili > ULN Treat as Grade 2 or 3-4 to 1.5 x ULN

Grade 2 · Delay I-O therapy per protocol AST or ALT > $3.0 \text{ to } \le 5 \text{ x}$ · Increase frequency of monitoring ULN and/or T. bili > 1.5 to every 3 days to ≤ 3 x ULN

> to every 1-2 days 1.0 to 2.0 mg/kg/day

equivalent*

Discontinue I-O therapy*

Increase frequency of monitoring

methylprednisolone IV or IV

opportunistic infections

· Consult gastroenterologist

Add prophylactic antibiotics for

•Resume routine monitoring, resume I-O therapy per protocol

If elevations persist > 5-7 days or worsen:

0.5-1 mg/kg/day methylprednisolone or oral equivalent and when LFT returns to grade 1 or baseline, taper steroids over at least 1 month, consider prophylactic antibiotics for opportunistic infections, and resume I-O therapy per protocol

If returns to grade 2:

If returns to baseline:

· Taper steroids over at least 1 month

If does not improve in >3-5 days, worsens or rebounds:

- Add mycophenolate mofetil 1 g BID
- If no response within an additional 3-5 days, consider other immunosuppressants per local guidelines

Patients on IV steroids may be switched to an equivalent dose of oral corticosteroids (e.g. prednisone) at start of tapering or earlier, once sustained clinical improvement is observed. Lower bioavailability of oral corticosteroids should be taken into account when switching to the equivalent dose of oral corticosteroids.

25-Jun-2019

Protocol Amendment No.: 09 Date: 14-Mar-2023

Grade 3-4

AST or ALT > 5 x ULN or

T.bili >3 x ULN

^{*}The recommended starting dose for grade 4 hepatitis is 2 mg/kg/day methylprednisolone IV.

[figure not shown]

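### For non-HCC participants, Section 7.5.3 and the Appendix 9 hepatic algorithm conflict on whether an isolated Grade 2 AST/ALT or bilirubin elevation requires a dose delay

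*Combined protocol and SAP*

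**What the plan says.** Section 7.5.3 lists the events for which all study treatment must be withheld. One entry is any drug-related non-skin event of Grade 2 or higher, with this exception: "Grade 2 drug-related fatigue or laboratory abnormalities do not require a treatment delay". The liver tests get their own delay rules for one group only: "Dose delay for AST, ALT, or total bilirubin abnormalities in HCC participants should be managed as follows". The first of those rules reads "If baseline AST, ALT, or bilirubin is within normal limits, delay dosing for Grade ≥ 2 toxicity". For everyone else the laboratory entry in the list is "Grade 3 laboratory abnormality, with the following exceptions", and none of the exceptions that follow concerns AST, ALT or bilirubin.

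Later in the same section the plan says that "all Grade 2 GI, renal, pulmonary, hepatic, and neurological AEs should be evaluated and managed per the toxicity management algorithms in Appendix 9".

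The standard hepatic algorithm in Appendix 9 is graded by liver-test elevation. Its Grade 2 action is "Delay I-O therapy per protocol", with more frequent monitoring, and its follow-up column describes resuming therapy once values return to baseline.

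Section 7.5.3.1 gives criteria for resuming after delays for drug-related AST, ALT or bilirubin elevations. It does not limit them to HCC; a separate sub-item covers HCC.

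**The concern.** A site that reads the exception in Section 7.5.3 may dose a non-HCC participant with a Grade 2 transaminase value. A site that follows the cross-reference to Appendix 9 will hold. The cross-reference does not settle the matter. The algorithm says to delay *per protocol*, the protocol text on delays is Section 7.5.3, and Section 7.5.3 points back to the algorithm.

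The question will arise in practice. The schedules of activities call for laboratory tests before each dose, and weekly in the early cycles, so these values will be in hand when the dosing decision is made. At stake is uniform handling of a liver signal in Part 2A and in the CRPC and TNBC cohorts of Part 2B, as well as in any Part 1 participants without HCC still on treatment.

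**Working it through.** No alpha, power or margin is involved, so the check compares texts. A frequency check follows.

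**Step 1. Range in question.** Appendix 9 puts Grade 1 at AST or ALT up to 3 × ULN or bilirubin up to 1.5 × ULN, and Grade 3-4 at AST or ALT above 5 × ULN or bilirubin above 3 × ULN. Grade 2 is therefore AST or ALT above 3 and up to 5 × ULN, and/or bilirubin above 1.5 and up to 3 × ULN. The columns of that table have run together in the available text, but the neighbouring rows fix the limits.

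**Step 2. Apply both texts to the same participant.** All cases are drug-related.

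| Case | Section 7.5.3 | Appendix 9, standard algorithm | Same requirement? |
|---|---|---|---|
| Non-HCC, AST 4 × ULN, no symptoms, normal bilirubin | Delay not required; allowed on judgment | Delay | No |
| Non-HCC, bilirubin 2 × ULN alone, no symptoms | Delay not required; allowed on judgment | Delay | No |
| Non-HCC, AST 4 × ULN with symptomatic liver inflammation | Withheld as potential DLT (7.5.1.2) | Delay | Yes |
| Non-HCC, AST 4 × ULN and bilirubin 2.5 × ULN, no cholestasis | Withheld as potential DLT (7.5.1.2) | Delay | Yes |
| HCC, normal baseline, AST 4 × ULN | Delay | Separate HCC algorithm, not legible in the available text | Not assessed |

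The conflict is confined to the first two rows.

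**Step 3. Look for a tie-breaker.** Section 7.5.3.1 presupposes that liver-test delays can occur outside HCC, but Grade 3 delays alone would account for that. No sentence gives either text precedence.

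**Step 4. Can the number affected be derived?** The nearest source is the CA209004 summary in Section 3.2.4 (53 participants on ipilimumab plus nivolumab). Treatment-related ALT increase was 21% at any grade and 11% at Grade 3-4; AST increase was 21% and 13%.

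- Worst grade below 3: ALT 21% − 11% = 10%; AST 21% − 13% = 8%.
- In an arm of 60 (Section 5.2), assuming equal rates: 0.10 × 60 = 6 for ALT; 0.08 × 60 = 4.8 for AST.
- These counts pool Grades 1 and 2. Participants with Grade 2 as worst grade could number anywhere from 0 to 6 for ALT and 0 to 4.8 for AST.
- Some Grade 3-4 cases may have passed through Grade 2. The any-grade ceiling on one test is 0.21 × 60 = 12.6.
- The overlap of ALT and AST is not given, and bilirubin is not listed.

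A span of 0 to 12.6 on a single test is not an estimate.

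**The case against.** The strongest defence is that the two texts differ in kind. Section 7.5.3 sets a minimum: it says a delay is not required, does not forbid one, and separately requires withholding for any laboratory abnormality that the investigator thinks warrants it. A site that holds breaks neither text. Appendix 9 calls itself guidance, its Grade 2 step defers to the protocol, and Section 7.5.2 says the nature of the events will determine how the algorithms are used. It could also be argued that Section 7.5.3 exempts laboratory values while Appendix 9 addresses hepatic adverse events.

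Part of this stands. A reader might infer two opposite rules, one commanding dosing and the other a hold. The documents do not support that; the disagreement is over whether a delay is required.

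The rest does not remove the conflict. If the algorithm deferred wholly to Section 7.5.3, its Grade 2 delay would be empty for an isolated laboratory rise in the very participants it serves, although its Grade 1 row says to continue and its Grade 2 follow-up speaks of resuming. The split between values and events fails because the algorithm is triggered by the liver-test value. Under Section 9.2.6, a laboratory result that led to interruption is itself reportable, so holding can decide whether an event is recorded.

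A reader might also infer that HCC participants face the stricter rule throughout. Under Section 7.5.3 that is so only for a normal baseline. With a Grade 1 baseline the HCC delay starts at Grade 3, the same laboratory threshold as for other participants.

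**Conclusion.** The concern holds within narrow limits: non-HCC participants with an isolated, asymptomatic, drug-related Grade 2 AST/ALT or bilirubin elevation that meets no DLT criterion. For them the plan gives conflicting answers on whether a delay is required and no order of precedence. It is an internal inconsistency in a safety rule and should be corrected.

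Two larger claims are tempting and not supported. One is a count of affected participants, such as 6 to 12 per arm. The cited study does not separate Grade 1 from Grade 2, and Section 8.1 predicts an attenuated immune-related profile for BMS-986249, so equal rates cannot be assumed for Arms C and F. The other is that the conflict distorts the primary safety endpoint. A Grade 2 value does not count in that endpoint (Table 4-4). Dosing or holding could affect whether Grade 3 is reached, and Part 2A is open-label, so an effect is possible. The documents give neither its size nor its direction.

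The conclusion rests on the wording alone and on reading Appendix 9 as the route that Section 7.5.3 prescribes for Grade 2 hepatic events.

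**What to change.** The sponsor must reconcile the exception and the cross-reference in Section 7.5.3, the resumption criteria in Section 7.5.3.1, and the Grade 2 row of the standard hepatic algorithm in Appendix 9. One rule for this case should then appear in the same words in Section 7.5.3 and Appendix 9, and sites should be notified in writing. The choice of rule belongs to the sponsor's safety team; this review does not say which is right.

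The HCC page of Appendix 9 cites Sections 7.4.3 and 7.4.3.1 for delay and resumption, while those rules now sit in 7.5.3 and 7.5.3.1. The numbers can be corrected at the same time.

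The cost is an administrative letter or an amendment sentence. It adds no visits, tests or analyses and leaves the sample size unchanged.
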